6.3. Outcome measures

Table 1 describes the outcome measures being used in this trial.

Table 1: Objectives, outcome measures and time-points

Objectives	Outcome Measures	Time-point(s) of evaluation of this outcome measure
Primary Objective		
To determine whether functional outcomes at four months after treatment in people with unstable ankle fractures managed with close contact casting are not worse than those treated with surgical intervention.	Olerud-Molander Ankle Score (OMAS) ²¹	4 months

Socondary Objectives		
Secondary Objectives		
To quantify and draw inferences on observed differences in ankle function	OMAS ²¹	8 weeks, 12 months
between the trial treatment groups	Ankle fracture outcome of rehabilitation measure (A-FORM) ²²	8 weeks, 4 months, 12 months
during the first year after treatment.	Global rating of change question (GRC) ²³	8 weeks, 4 months, 12 months
2. To estimate differences in health-	EuroQol EQ-5D-5L ²⁴ health-related quality of	8 weeks, 4 months,
related quality of life between the trial	life instrument	12 months
treatment groups in the first 12 months post-treatment.	The Work Productivity and Activity Impairment Questionnaire (WPAI) 25	
3. To determine the risk of complications between the trial treatment groups in the first 12 months post-treatment.	Self-report questionnaires & medical notes: All potentially related adverse events including infection, symptomatic deep vein thrombosis, pulmonary embolus and unplanned return to theatre. Radiographs (routinely collected radiographs will be harvested):	8 weeks, 4 months, 12 months
	Fracture displacement, non-union, mal-union	
4. To estimate the resource use, costs and comparative cost effectiveness between the trial treatment groups at 12 months post-treatment.	Review of medical notes by research nurses at all trial centres complemented by bespoke resource use questionnaires administered to patients	6 weeks, 12 months,
5. To investigate the difference in ankle	Hospital Episode Statistics: inpatient,	
function, the risk of late adverse events and comparative cost effectiveness between the trial treatment groups within 5 years.	outpatient & emergency department databases OMAS ²¹	Annually until 5 years post-treatment
	A-FORM ²²	
	EQ-5D-5L ²⁴	
	Global rating of change question (GRC) ²³	
	Related adverse events from bespoke questionnaires administered to patients	

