9.6.1. Surgical treatment

Participants will undergo internal fixation of their fracture. The peri-operative care, for example pre-operative assessments, type of anaesthesia and the selection of antibiotics will be in accordance with local protocols. The selection of the operating position, the use of a tourniquet, approach, implants and surgical technique will be at the discretion of the treating surgeon. The specific technique and implants used by the treating surgeon will be recorded. Equally the application of any immobilising devices, such as cast or a walking boot, will also be recorded.

Participants' post-operative weight-bearing instructions will be left to the discretion of the treating surgeon, but all details will be recorded.

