9.6.2. Non-surgical treatment

Participants will undergo close contact casting (CCC). Close contact casting is now an established intervention and is recommended as the primary treatment for adults over 60 years of age with unstable fractures in the current NICE guidance.⁶

In consultation with patients and patient representatives during the development of the trial protocol, and in common with the established practice for older adults based upon the non-surgical intervention tested in the AIM trial,³ all initial manipulations and applications of CCC will take place under anaesthesia.

The method of closed fracture manipulative reduction of deformity under image intensifier guidance will be left to individual surgeons and this falls within the common contemporary skills set of trauma and orthopaedic surgeons. The anaesthetic technique will be left to the discretion of the treating anaesthetist.

The CCC will be applied to the ankle once, in the opinion of the treating surgeon, the fracture has been adequately reduced. There will be standardisation of the casting materials, cast design and application, and moulding technique, as per the AIM trial training package.³ This technique will be revisited with clinical teams at each site with the FAME training team. In the event that an acceptable closed reduction cannot be achieved then the operating surgeon will proceed to open reduction and internal fixation (ORIF) if this is clinically appropriate. Conversion to ORIF in these circumstances, where an acceptable reduction cannot be achieved or maintained intraoperatively, will not constitute a protocol violation. Details of the reasons and the surgical technique used will be recorded.

Participants will be non-weight bearing for the duration of the CCC treatment.

The clinical follow-up schedule in the early phase will be left to the discretion of the treating surgeon. It is anticipated that some participants will require repeat applications of the CCC as the swelling around the injured ankle reduces. Subsequent applications of the CCC can be performed outside of an operating theatre, for example in plaster rooms. Advice regarding the frequency of clinical monitoring will be provided in the training sessions and rehabilitation booklet. After reapplications of the CCC repeat radiographs will be performed to confirm the reduction has been maintained.

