10.3. Reporting Procedures for Adverse Events not defined as serious

Adverse events that are unrelated to the intervention or treatment will not be reported.

Adverse events (AEs) that are foreseeable in the treatment of these fractures, and are not defined as SAEs, do not need to be reported immediately, provided they are recorded in the 'Complications' section of the Case Report Forms and/or Patient Questionnaires.

Other adverse events, foreseeable or unforeseeable, that are not in this list, will not be reported.

Foreseeable, related AEs include the following:

- (a) Related to CCC only:
- o loose cast or tight cast requiring reapplication
- failed closed reduction
- o pressure ulcer
- o plaster saw laceration
- (b) Related to surgical treatment only:
- o surgical site infection
- failed fixation
- o prominent implant
- wound dehiscence
- vascular injury

- (c) Related to both treatments:
- o revision surgery, defined as unplanned return to theatre
- symptomatic deep venous thrombosis
- o symptomatic pulmonary embolus
- o compartment syndrome
- o nerve palsy
- o complex regional pain syndrome
- pain/irritation/itchiness from cast

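### Cast reapplication is both an anticipated part of close contact casting and a casting-only adverse event, with no rule separating the two and no matching category for casts in the surgical arm

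*Protocol*

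**What the plan says.** Protocol section 9.6.2, on the casting pathway, states: "It is anticipated that some participants will require repeat applications of the CCC as the swelling around the injured ankle reduces". It continues: "Subsequent applications of the CCC can be performed outside of an operating theatre, for example in plaster rooms". Later casts may therefore be applied in theatre or elsewhere. No recast rate or casting schedule is given.

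Section 10.3 groups the foreseeable related adverse events. The first item under CCC only is "loose cast or tight cast requiring reapplication". The group for both treatments includes "revision surgery, defined as unplanned return to theatre". Foreseeable events that are not serious need no immediate report, "provided they are recorded in the 'Complications' section of the Case Report Forms and/or Patient Questionnaires". The section adds that adverse events outside its list go unreported.

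Table 1 in section 6.3 states secondary objective 3 as "To determine the risk of complications between the trial treatment groups in the first 12 months post-treatment". Its adverse-event measure is "All potentially related adverse events including infection, symptomatic deep vein thrombosis, pulmonary embolus and unplanned return to theatre".

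For the surgical arm, section 9.6.1 says: "Equally the application of any immobilising devices, such as cast or a walking boot, will also be recorded". Section 10.3 also places cast discomfort in the group for both treatments, so the protocol accepts that casts are worn in both arms.

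**The concern.** A cast changed because swelling has gone down is, in ordinary terms, often a loose cast being re-applied. Section 9.6.2 treats that as expected delivery of the allocated treatment, and section 10.3 treats it as a related adverse event. Sites have no rule for choosing between the two and may choose differently.

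The item also runs one way. A loose or tight cast after fixation is physically the same problem, but the list gives it no place. Collection is therefore unequal by arm, before any analysis choice is made.

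The place of the recast can change its label as well. Revision surgery is defined by an unplanned return to theatre, with no exception for a closed recast, so such an event could share a category with re-operation for failed fixation.

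This matters because section 5.1 gives avoidance of surgical complications as the key benefit of non-surgical treatment, and objective 3 is where the trial measures complications. If recasts are recorded in one arm only and without a reason, later analysis can drop the whole item. It cannot recover the missing surgical-arm recasts or sort expected changes from problems.

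**Working it through.** **Text check.** How different recasts fall under the current wording:

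| Recast | Section 9.6.2 | Cast item in 10.3 | Revision surgery in 10.3 |
|---|---|---|---|
| CCC arm, loose as swelling falls, plaster room | Anticipated | Yes, literally | No |
| CCC arm, tight cast, plaster room | Not explained by falling swelling | Yes | No |
| CCC arm, recast planned in theatre | Not excluded | Yes, if loose or tight | No, because planned |
| CCC arm, unplanned closed recast in theatre | Not excluded | Yes, if loose or tight | Yes, literally |
| Surgical arm, loose or tight post-operative cast, plaster room | Does not apply | No listed category | No |

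The first row shows the overlap. The first and last rows together show the asymmetry.

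**Illustrative size.** The protocol states no figure for the complication comparison, so there is none to reproduce. The 400 per arm used here comes from the primary sample size in section 11.2 (SD 21.8, margin 5, 90% power, one-sided 2.5%):

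- n per arm = 2 × 21.8² × (1.960 + 1.282)² / 5² ≈ 399.5, rounded up to 400, which gives the stated 800.
- 800 / 0.90 = 888.9, against the stated 890.

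That calculation reproduces, and the present point does not depend on it.

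Assumptions that are not in the documents:

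- risk p of any other complication, equal in both arms: 15%, with a range of 10–20%;
- recast rate r, counted in the CCC arm only: 5–10%, with 2% also shown;
- recasts independent of other complications;
- one pooled any-complication endpoint with 400 analysed per arm.

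Recorded CCC risk = 1 − (1 − p)(1 − r), so the artificial excess is r(1 − p).

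At p = 15%:

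- r = 2%: 1 − 0.85 × 0.98 = 16.7%, an excess of 1.7 points.
- r = 5%: 1 − 0.85 × 0.95 = 19.25%, an excess of 4.25 points.
- r = 10%: 1 − 0.85 × 0.90 = 23.5%, an excess of 8.5 points.

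Across p = 10% to 20%, the excess runs from 4.5 down to 4.0 points at r = 5%, and from 9.0 down to 8.0 points at r = 10%.

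The chance of a nominally significant result against CCC, at the two-sided 5% level that section 11.8 sets for secondary outcomes, is Φ[(d − 1.96 × SE₀) / SE₁]. Here d is the excess, SE₀ the pooled standard error and SE₁ the unpooled one. At p = 15%:

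- r = 2%: 10%.
- r = 5%: d = 0.0425, SE₀ = 0.02664, SE₁ = 0.02660, giving 36%.
- r = 10%: d = 0.085, SE₀ = 0.02788, SE₁ = 0.02772, giving 86%.

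Over p = 10% to 20%, the chance is 49% to 28% at r = 5% and 95% to 76% at r = 10%. If the item stays outside the pooled count, this artefact is zero.

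**The case against.** The strongest reply is that anticipating an event does not stop it being an adverse event. Section 10.3 is openly a list of foreseeable events, and failed closed reduction follows the same pattern: section 9.6.2 provides for it and section 10.3 still lists it. The listed item is also broader than the anticipated step, since falling swelling does not explain a tight cast, and not every repeat cast need be loose or tight. All of this stands. It is why the item should remain recorded safety data. Removing it altogether would favour the casting arm in a trial that section 9.5 says cannot be blinded.

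A second reply is that no composite is defined and that section 11.1 leaves analysis detail to the statistical and health economics analysis plan. This also stands. A reader might infer that the protocol counts routine delivery as harm, but that is only what the wording permits if events are pooled. Reported item by item, recasts distort no other line. The reply does not reach the collection problem, because the event list itself decides what sites enter in each arm.

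A third reply is that few recasts would be revision surgery. That is right: the definition needs a return to theatre that is unplanned, and no text suggests this would be common. The gap is only that no exception is written for it.

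**Conclusion.** The point holds as a conflict of definitions and a one-sided count. Sections 9.6.2 and 10.3 give the same cast change two statuses without a dividing rule, and a recast in a surgical participant has no listed category. Any pooled complication comparison would therefore count recasts in the casting arm only. The revision-surgery overlap is confined to unplanned closed recasts in theatre.

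The size is unknown. The excess of about 4 to 8.5 points rests on an assumed 5–10% recast rate, an assumed equal 15% risk of other complications, independence, 400 per arm, and a pooled endpoint that the protocol does not define.

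A reader might go further and infer that an apparent safety benefit of casting would turn into an excess. The documents do not support that, because they give neither a recast rate nor an overall complication risk for either arm. Nor can the surgical rates in section 5.1 (1 + 9.1 + 1.7 + 1.3 + 2.7 = 15.8%) be summed into a ceiling for the surgical arm. They omit events listed in section 10.3 such as thrombosis and nerve palsy, and section 5.3 says that surgical complication risk in younger, fitter adults may be lower.

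**What to change.** Reconcile sections 9.6.2 and 10.3 on recording and reporting only:

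- Keep loose or tight casts as recorded safety data.
- Record every cast reapplication in both arms, including post-operative casts in the surgical arm, with its reason (expected change as swelling falls, or a loose or tight cast problem) and its place.
- Report reapplication as its own category outside any pooled complication count, or show that count with and without it.
- State in section 10.3 and Table 1 that a closed recast without fixation is reported separately from revision surgery.
- Leave cast injuries, such as pressure ulcer and plaster saw laceration, as complications.

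Nothing changes in when, where or how casts are re-applied. The cost is some wording and a small change to the case report form. The downside is that cast changes leave any headline complication count, although they are still reported in full.

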11. STATISTICS AND ANALYSIS

All available data from both treatment arms will be used in data analysis. Reporting of the results will be in accordance with the CONSORT statement ³¹ using the extensions for non-pharmacological treatment interventions and patient-reported outcomes. Baseline demographic data will be summarised to check comparability between treatment arms. Standard statistical summaries and graphical plots will be presented for the primary outcome measure and all secondary outcome measures. Differences between treatment groups will be assessed on both an intention-to-treat and per protocol basis, using a normal approximation for the OMAS score, ²¹ at four months post-treatment, and at additional time-points.

11.1. Statistical & Health Economics Analysis Plan

A statistical and health economic analysis plan (SHEAP) with full details of all analyses will be drafted early in the trial and finalised prior to primary outcome analysis. The SHEAP will be reviewed and will receive input from the Trial Steering Committee (TSC) and the Data Safety and Monitoring Committee (DSMC). Any changes or deviations from the original SHEAP will be described and justified in the protocol, an updated SHEAP, final report and publications as applicable, depending on the timing of the changes. Interim analyses of efficacy outcomes are not planned and will be performed only where requested by the DSMC. Following a blinded analysis of the data, undertaken prior to the final data-lock, the per-protocol population will be finalised and the SHEAP updated. It is anticipated that all analysis will be undertaken using Stata (StataCorp LP, www.stata.com) or other well-validated statistical packages.

11.2. Sample Size Determination

The primary clinical outcome is OMAS at 4 months. Previous studies have demonstrated a minimally clinical important difference (MCID) of 10 points, ^{3 32} which is in accordance with expert opinion (for scales scoring 0-100) and statistical convention. ^{3 33} We have selected a standard deviation (SD) of 21.8 based on the largest published RCT studying the OMAS within six months of surgically treated ankle fracture. ³ Although AIM included participants aged over 60 years we are not expecting the variability in OMAS in participants aged 60 years and younger to be different. A non-inferiority margin of 5 points has been chosen. This is half the MCID (one method of choosing the non-inferiority margin) and this has been discussed with clinical experts who felt that this would provide enough evidence to change clinical practice, whereas using 6 points (as AIM used for its equivalence margin) would be less convincing in this patient population.

800 participants providing data at four months will provide 90% power and 2.5% (1-sided) significance to detect whether non-surgical treatment for the treatment of unstable ankle fractures is non-inferior to surgical treatment using a non-inferiority margin of -5 points on the OMAS score at four months. Allowing for 10% loss to follow-up, this yields an overall target of 890 participants (445 per arm). ³⁴ Essentially the lower 95% confidence interval of the treatment difference is assessed against the non-inferiority margin

of -5 points and if it lies above this then the trial will be assessed as non-inferior. If non-surgical management is found to be non-inferior to surgical management of unstable ankle fractures then superiority will also be tested at 2.5% (1-sided) significance (the equivalent of comparing the lower 95% confidence interval against Zero rather than -5 points).

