11.3. Analysis populations

The per protocol (PP) population will include all patients who received their allocated treatment and did not have any major protocol deviations with available data at all time-points up to and including 12 months. Major protocol deviations will be pre-specified in the Data Management Plan and SHEAP and finalised following a blinded review of the data prior to the primary outcome analysis data-lock.

The Intention-to-Treat (ITT) population will include all participants with available data at all time-points up to and including 12 months in the randomised groups to which they were allocated regardless of which treatment they actually received.

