11.4. Description of the Statistical Methods

In non-inferiority trials we want to show that the new treatment is not clinically worse than the active control and therefore the interest is one-sided. The new treatment may be better than the control, but it is at least non-inferior to it. We define a non-inferiority margin (Δ_T), which is the maximum difference we are prepared to tolerate in a given direction that the new treatment is not to be considered clinically inferior to the well-established standard treatment. The null hypothesis is therefore that a difference of greater than Δ_T exists in favour of the standard treatment (H₀: $\Delta \le -\Delta_T$) (Δ defined as the difference between treatment and control (T-C)) and the trial is targeted at disproving this in favour of the alternative that the new treatment is non-inferior (H_A : $\Delta \ge -\Delta_T$). This will be assessed by creating a 95% confidence interval which should be entirely above the non-inferiority margin for the new treatment to be declared noninferior. FDA regulations recommend that both a treatment received (per protocol) and intention to treat (ITT) analysis is performed aiming to demonstrate non-inferiority. Use of the ITT approach as in a superiority trial sometimes increases the chance of falsely claiming non-inferiority. Therefore, the primary analysis will be undertaken on the per-protocol population, where only those patients who received their allocated treatment will be analysed and those that do not will be excluded from the analysis. A secondary analysis will be undertaken on the ITT population where all randomised patients will be analysed according to their treatment allocation.

The result of the analysis for the primary endpoint should be one of the following:

- The confidence interval for the difference between the two treatments lies entirely above the noninferiority margin (-ΔT), so that non-inferiority may be concluded with only a small probability of error.
- The confidence interval includes points below the non-inferiority margin, then there is a possibility that the new treatment is inferior to the control and non-inferiority cannot be safely concluded.
- The confidence interval is entirely above zero, indicative of a treatment effect, then superiority of the new treatment can be concluded within a small probability of error.

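### The 890 target is inflated only for loss to follow-up, so at the planned 10% loss the per-protocol primary analysis has less than the stated 90% power once exclusions are material

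*Protocol*

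**What the plan says.** Protocol section 11.2 fixes the endpoint ("The primary clinical outcome is OMAS at 4 months"), the variability ("We have selected a standard deviation (SD) of 21.8") and the margin ("A non-inferiority margin of 5 points has been chosen"). It then states that "800 participants providing data at four months will provide 90% power and 2.5% (1-sided) significance", and it inflates once: "Allowing for 10% loss to follow-up, this yields an overall target of 890 participants (445 per arm". It names no other source of attrition.

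Section 11.4 chooses the analysis that decides the trial: "Therefore, the primary analysis will be undertaken on the per-protocol population". It adds that participants who did not receive their allocated treatment are left out, and later says that the adjusted per-protocol analysis determines non-inferiority and then superiority. Intention-to-treat is supporting.

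Section 11.3 limits the per-protocol set to "all patients who received their allocated treatment and did not have any major protocol deviations" and, read literally, to those with data at all time-points up to 12 months. It applies the same data condition to the intention-to-treat set. Major deviations are left to the Data Management Plan and the SHEAP.

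Section 9.6.2 says that conversion from casting to internal fixation during the procedure, where closed reduction fails, is not a protocol violation.

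**The concern.** Section 11.2 describes everyone with a four-month score, whereas the trial is decided on a subset of those people. The 10% inflation is spent entirely on missing outcome data. Participants who have a four-month score but are removed for treatment received or for deviations are not allowed for.

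Some exclusions are foreseeable. The trial compares surgery with casting without blinding (section 9.5), section 5.1 acknowledges difficulties with surgeon equipoise, and section 11.3 provides for major deviations to be identified.

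What is at stake is how a negative result is read. If the per-protocol interval crosses -5, readers will set that against a 90% power figure which the per-protocol set may not have had. They may then put down to inferiority what is partly imprecision.

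**Working it through.** **Inputs.** From section 11.2: SD 21.8, margin 5, one-sided 2.5%, power 90%, 10% loss, target 890. From section 7: 1:1 allocation. The true difference is not stated. I take it as 0, which reproduces the plan's figure.

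**Step 1: reproduce the plan.**

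n per arm = 2 × SD² × (1.960 + 1.282)² / margin² = 2 × 475.24 × 3.2415² / 25 = 399.5, so 400 per arm and 800 in total.

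Power with 400 per arm is 90.0% (normal approximation 90.04%, noncentral t 89.97%).

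Inflation: 800 / 0.9 = 888.9, so 889, rounded to 890 for equal arms. The stated figures are correct.

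**Step 2: slack at the planned loss.** 890 × 0.9 = 801, or 400.5 per arm, with power 90.1%. That is one participant above 800.

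**Step 3: power after per-protocol exclusions.** Let e be the proportion of those with four-month data who are excluded. The protocol gives no value, so every e below is an assumption.

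Power = Φ( 5 / (21.8 × √(1/n₁ + 1/n₂)) − 1.96 )

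Worked case, e = 10% in both arms: n₁ = n₂ = 400.5 × 0.9 = 360.45; standard error = 21.8 × √(2/360.45) = 1.624; 5/1.624 = 3.079; Φ(3.079 − 1.960) = Φ(1.119) = 86.8%.

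| Assumed e | Analysed, both arms excluded | Power | Power, casting arm only | Randomised to keep 800 if both arms excluded |
|---|---|---|---|---|
| 5% | 761 | 88.6% | 89.3% | 936 |
| 10% | 721 | 86.8% | 88.5% | 988 |
| 15% | 681 | 84.9% | 87.5% | 1,046 |
| 20% | 641 | 82.7% | 86.4% | 1,112 |

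The last column is 800 / (0.9 × (1 − e)), rounded up. Power drops below 88% at about 7% exclusions in both arms.

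**Step 4: the data condition in section 11.3.** The 10% in section 11.2 concerns four-month data. If completeness to 12 months is required and 15% are incomplete by then (assumed), 890 × 0.85 = 756.5 remain and power is 88.4% before any other exclusion. A further 10% excluded leaves 681 and 84.9%.

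**Step 5: possible gain from covariate adjustment.** Section 11.4 adjusts for baseline OMAS, age, gender and fracture stability. With a correlation r between covariates and outcome, the residual SD is 21.8 × √(1 − r²). For an assumed r = 0.3 this is 20.8, and exclusions of 10% and 20% in both arms give 89.8% and 86.1%.

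**The case against.** A reader might infer that section 11.2 contains an arithmetic error. It does not: all its figures reproduce. Its sentence is also conditional. It says what 800 participants with data would provide, which is true, and nowhere says outright that the per-protocol set has 90% power. That link comes from reading it with section 11.4. It is still the natural reading, because section 11.2 offers no other power figure for the analysis that decides the trial.

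A reader might also infer that 800 can be reached only with no exclusions at all. That holds only if the full 10% is lost. With 5% loss, 845.5 have data and 5.4% could be excluded with 800 left; with 7% loss, 827.7 have data and 3.3% could be.

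Nor do the documents support counting every intra-operative conversion as an exclusion. Section 9.6.2 says that these are not violations, while section 11.4 excludes anyone who did not receive the allocated treatment. The sections pull in different directions.

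The loss is small at low rates (2% in both arms gives 89.5%), and nothing in the protocol supports 15% or 20% in particular. Adjustment could offset some or all of it: on the figures above, r = 0.3 nearly cancels 10% exclusions. But the protocol gives no correlation and takes no credit for one, so this is as much an assumption as the exclusion rate.

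Finally, section 11.4 already separates failure to show non-inferiority from demonstrated inferiority, which limits the harm. The definition of major deviations may properly be left to the SHEAP. The inflation and the power statement are fixed here.

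**Conclusion.** The point holds as a mismatch between the set that was sized and the set that decides the trial. At the plan's own 10% loss, any material per-protocol exclusion puts the primary analysis below 90% power.

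The size is modest and cannot be fixed from the protocol. It is about 1.5 to 7 percentage points for assumed exclusions of 5% to 20% in both arms, and less if only the casting arm is affected. These figures assume SD 21.8, true difference 0, exactly 10% loss and no gain from covariates. Lower loss or useful covariates would shrink the shortfall; a literal requirement for data to 12 months could enlarge it.

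This does not show that the trial is too small to be useful, and it is no reason to demand more participants. The power statement should be corrected.

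**What to change.** Keep 890.

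- **Section 11.2:** state that 90% power applies to 800 participants analysed with four-month OMAS. Add the per-protocol power at 890 over a range of exclusion rates, labelled as assumptions, for example 88.6% at 5% down to 82.7% at 20% in both arms. Do not call the 800 the intention-to-treat set while section 11.3 ties that set to data through 12 months. If credit for covariate adjustment is wanted, state the assumed correlation.
- **Section 11.3:** for the four-month primary analysis, define both analysis sets by availability of four-month OMAS rather than by data at all time-points to 12 months.
- **Sections 9.6.2, 11.3 and 11.4:** reconcile whether an intra-operative conversion counts, for the analysis, as having received the allocated treatment. How much of the shortfall this or the section 11.3 change would remove cannot be said, because the protocol gives no rate for either.

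The cost is a few sentences and no extra patients. The stated power of the primary analysis becomes slightly less favourable.
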